#### **5.1.2.6. Increases in Urinary Protein**

Increases in urinary albumin have been observed in some patients treated with bardoxolone methyl with CKD and type 2 diabetes. The increases are likely due to bardoxolone methyl's pharmacological modulation of tubular protein reabsorption and have not been associated with interstitial fibrosis or injury. In preclinical studies, bardoxolone methyl has been shown to downregulate the primary proteins involved in protein reabsorption in the proximal tubules: the megalin-cubilin complex. Moreover, the magnitude of observed eGFR increases with bardoxolone methyl treatment is thought to reduce the residence time of protein in the proximal tubules, thereby reducing protein reuptake and increasing urinary protein levels. Therefore, increased eGFR, together with decreased megalin expression, is thought to result in decreased fractional absorption of albumin and increased urinary excretion of albumin. Consistent with bardoxolone methyl-mediated protection in preclinical models of protein-overload-induced nephropathy, these pharmacological effects are thought to reduce protein overload and secondary nephropathy caused by excessive albumin uptake and therefore are not associated with tissue injury and interstitial fibrosis.

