6.5.4.1. Prognosis of CKD by eGFR and Albuminuria Category

Prognosis of chronic kidney disease (CKD) is determined by the intersection of the following eGFR and albuminuria categories ([KDIGO, 2013](#)):

Figure 2: PROGNOSIS OF CKD BY eGFR AND ALBUMINURIA CATEGORIES

				Persistent albuminuria categories Description and range		
				A1	A2	A3
				Normal to mildly increased	Moderately increased	Severely increased
				<30 mg/g <3 mg/mmol	30–300 mg/g 3–30 mg/mmol	>300 mg/g >30 mg/mmol
GFR categories (ml/min per 1.73 m ²) Description and range	G1	Normal or high	≥90			
	G2	Mildly decreased	60–89			
	G3a	Mildly to moderately decreased	45–59			
	G3b	Moderately to severely decreased	30–44			
	G4	Severely decreased	15–29			
	G5	Kidney failure	<15			

Green: low risk (if no other markers of kidney disease, no CKD); yellow: moderately increased risk; orange: high risk; red, very high risk.

The Prognosis of Kidney Disease: Improving Global Outcomes (KDIGO) CKD progression risk scores is summarized by cell and color (Green, Yellow, Orange and Red).

Table 6. CKD STAGE

CKD ^a Stage	eGFR ^b (mL/min/1.73 m ²)
1	≥90
2	60 to <90
3a	45 to <60
3b	30 to <45
4	15 to <30
5	<15

^a Chronic kidney disease

^b Estimated glomerular filtration rate

Table 7. ALBUMINURIA CATEGORY

ACR ^a Category	ACR (mg/g)
1 (normo-albuminuria)	<30
2 (micro-albuminuria)	30 to ≤300
3 (macro-albuminuria)	>300

^a Urine albumin to creatinine ratio

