6.5.5.1. Baseline Urine Albumin to Creatinine Ratio (ACR) Categorical Status

Baseline ACR status will be grouped by the following categories using baseline ACR (see Section 6.4.5):

- ACR ≤300 mg/g
- ACR >300 mg/g

Baseline ACR accounts for screening and Day 1 values and may not match ACR used for stratification based on screening values only.

6.5.5.2. eGFR Category used in Stratification (eGFR_STRAT)

The eGFR category used for stratification (eGFR_STRAT) is determined by the randomization list with the following categories:

- 30 mL/min/1.73 m²<eGFR<60 mL/min/1.73 m²
- 60 mL/min/1.73 m²≤eGFR≤90 mL/min/1.73 m²

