7.3. Demographic and Baseline Characteristics

Summaries of demographic and other baseline characteristic data are presented by treatment group for all analysis populations. They may also be summarized by randomized dose level (20 mg, 30 mg, or placebo).

The demographic and other baseline characteristics include:

- Baseline Age, Baseline Age category (<18, ≥18)
- Sex, Race, Ethnicity
- Weight (kg), Height (cm), BMI (kg/m²)
- Diastolic and systolic blood pressure (mmHg), Heart rate (bpm)
- Serum creatinine, eGFR, eGFR categorical status (<60, ≥60), eGFR Stratum
- ACR, ACR categorical status (≤300; >300), ACR Stratum
- KDIGO CKD progression risk score: color (Green, Yellow, Orange, Red) and cell in [Figure 2](#)
- CKD Stage ([Table 6](#))
- Angiotensin converting enzyme inhibitor (ACEi) treatment and/or Angiotensin II receptor blocker (ARB) (yes/no)
- Other baseline variables of interest

ADPKD related information includes:

- Age at ADPKD diagnosis
- Family history of ADPKD
- For patients with family history of ADPKD:
 - Sonography (indicating 3 or more cysts) for adult patients
 - Sonography (indicating 1 or more cyst) for adolescent patients
 - Computed tomography (CT) or magnetic resonance imaging (MRI) (indicating 5 or more cysts)
- For patients without family history of ADPKD:
 - Other cystic kidney diseases present
 - 10 or more cysts
- Use of Tolvaptan
 - Currently using Tolvaptan
 - Previously used Tolvaptan
 - Never received Tolvaptan
- [REDACTED]

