9.5.1. Continuous Summaries of Laboratory Results

Laboratory evaluations and change from baseline are summarized by treatment, laboratory category (hematology, chemistry, urinalysis, and microscopy), test, and study visit using continuous statistics. The eGFR results are calculated using formulas described in Section 6.5.4.

Chemistry values (including eGFR) collected at the following visits will be averaged.

- Week 104 A and Week 104 B
- Week 108 A and Week 108 B
- Week 112 A and Week 112 B

Box plots and line graphs are generated for selected laboratory test results, such as eGFR, ACR, alanine aminotransferase (ALT), aspartate aminotransferase (AST), TBL, BNP, blood urea nitrogen, uric acid, magnesium, creatinine, and creatine kinase (CK). Line graphs include mean \pm SE over time for both the observed values and for change from baseline.

Summaries of continuous statistics are provided for the following urinalysis parameters: albumin, creatinine, pH, erythrocytes, and specific gravity. Qualitative lab results are included in the listings but are not summarized. Laboratory results that are above or below normal limits are flagged in the listings. Summaries of ACR (Section 6.5.5) will use the geometric mean (with standard error) with 95% confidence intervals instead of the arithmetic mean and will display ACR results in original units of mg/g. Changes from baseline in ACR are calculated as the ratio of each visit to baseline and reported as the post-baseline/baseline ratios and are summarized by geometric means with 95% confidence intervals at each time point.

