9.5.2. Categorical Summaries of Laboratory Results

Select laboratory parameters will be summarized using shift tables. Shift tables are summarized by treatment, laboratory category (hematology, chemistry, urinalysis, and microscopy), and laboratory test and present shifts from baseline status (Normal, Low, High) to worst on study treatment status (Normal, Low, High). The worst abnormality values are defined as the maximum values while on study treatment (i.e., up to <21 days after last dose), with the exception of magnesium and hemoglobin. The worst abnormal values for magnesium and hemoglobin are defined as the minimum values while on study treatment (i.e., up to <21 days after last dose).

Additionally, laboratory parameters of specific interest (ALT, AST, ACR, BNP) are summarized using shift tables that summarize shifts from (1) baseline status to end of treatment status, (2) worst on-treatment status to worst off-treatment status, (3) worst on-treatment status to end of study, and (4) baseline status to worst on-treatment status 5) baseline to worst off-treatment, and (6) worst on-treatment status to best (lowest) off-treatment status. The number and percentage of patients are summarized. For ACR, summaries will present shifts from/to the categories listed in Section 6.5.5.1. For ALT and AST, summaries will present shifts from/to the following categories:

- \leq ULN
- $>$ ULN to $<3 \times$ ULN
- $\geq 3 \times$ ULN to $<5 \times$ ULN
- $\geq 5 \times$ ULN to $<10 \times$ ULN
- $\geq 10 \times$ ULN to $<20 \times$ ULN
- $\geq 20 \times$ ULN

For BNP, summaries will present shifts from/to the following categories:

- <100 pg/mL
- ≥ 100 pg/ml to <200 pg/ml
- ≥ 200 pg/ml to <400 pg/ml
- ≥ 400 pg/ml

In addition, a summary table is provided for the number and percentage of patients meeting a following pre-specified threshold level at any time during the study:

- ACR >3500 mg/g
- Magnesium <1.3 mEq/L (0.65 mmol/L)
- BNP >200 pg/mL
- NT-proBNP >1000 pg/mL

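### The six ACR shift tables in SAP 9.5.2 use only a 300 mg/g cut, so they do not count patients who cross 30 mg/g, although SAP Table 7 already defines that category

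*SAP*

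**What the plan says.** SAP 9.5.2 states that "laboratory parameters of specific interest (ALT, AST, ACR, BNP) are summarized using shift tables". It lists six comparisons: baseline to end of treatment, worst on-treatment to worst off-treatment, worst on-treatment to end of study, baseline to worst on-treatment, baseline to worst off-treatment, and worst on-treatment to best off-treatment.

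The ACR categories come by cross-reference: "For ACR, summaries will present shifts from/to the categories listed in Section 6.5.5.1". SAP 6.5.5.1 is a baseline definition ("Baseline ACR status will be grouped by the following categories using baseline ACR") and offers two groups, ≤300 and >300 mg/g. The same cut defines the randomisation stratum (SAP 6.5.5.3) and the maximum-dose group (SAP 4.1).

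SAP 6.5.4.1, Table 7, has a three-level scale: normo-albuminuria below 30, micro-albuminuria from 30 up to and including 300, and macro-albuminuria above 300 mg/g. In the readable text that scale is used only at baseline, through the entry in SAP 7.3 that reads "KDIGO CKD progression risk score: color (Green, Yellow, Orange, Red) and cell in" Figure 2.

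On the drug, Protocol 5.1.2.6 reports: "Increases in urinary albumin have been observed in some patients treated with bardoxolone methyl with CKD and type 2 diabetes".

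Two other ACR outputs are visible. SAP 9.5.1 gives continuous summaries ("Changes from baseline in ACR are calculated as the ratio of each visit to baseline", reported as geometric means with 95% confidence intervals) and names ACR for box plots and line graphs. SAP 9.5.2 counts patients with ACR above 3500 mg/g.

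**The concern.** A shift table is there to show how many patients change category and in which direction. For ACR, the categories were built for dosing and stratification and then reused as a scale of change on treatment. Everyone from zero to 300 mg/g sits in one cell, so movement between normo- and micro-albuminuria leaves no trace in any of the six tables. That includes recovery after stopping drug, which the comparison with best off-treatment status is suited to show.

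The treatment of ACR is also uneven within its own paragraph. ALT and AST have six categories and BNP has four; ACR has two. Elsewhere the protocol treats 30 mg/g as a meaningful level: Protocol 9.1.7 sets different blood pressure targets on either side of it. What is at stake is a set of patient counts by arm for a laboratory effect that the protocol itself describes.

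**Working it through.** The plan states no figure on this point, so there is nothing to reproduce. The check is to classify the same ACR pairs under both rules.

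**Inputs**
- Rule A, SAP 6.5.5.1: ≤300; >300 mg/g.
- Rule B, SAP Table 7: <30 (level 1); 30 to ≤300 (level 2); >300 (level 3).
- The ACR pairs are illustrative assumptions, not trial data.

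| From → to (mg/g) | Ratio | Rule A | Rule B |
|---|---|---|---|
| 10 → 40 | 4.0 | no change | 1 → 2 |
| 15 → 150 | 10.0 | no change | 1 → 2 |
| 29 → 300 | 10.3 | no change | 1 → 2 |
| 10 → 300 | 30.0 | no change | 1 → 2 |
| 200 → 20 | 0.1 | no change | 2 → 1 |
| 100 → 290 | 2.9 | no change | no change |
| 290 → 310 | 1.1 | shift | 2 → 3 |
| 20 → 310 | 15.5 | shift | 1 → 3 |
| 310 → 3500 | 11.3 | no change | no change |

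**Smallest rise that registers from below 30.** Under Rule A the later value must exceed 300 while the starting value is under 30, so the ratio must exceed 300/30 = 10.

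**Table size.** Rule A gives 2 × 2 = 4 cells, of which 2 are off the diagonal. Rule B gives 3 × 3 = 9 cells, of which 6 are off the diagonal.

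**Nothing is lost by changing.** Both rules share the 300 boundary. Adding the four Rule B cells formed by levels 1 and 2 gives the Rule A cell for ≤300 at both times, and the other cells collapse in the same way.

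**Whether another readable output counts crossings of 30 mg/g.** The >3500 mg/g count cannot; it lies above even the 2500 mg/g entry limit in Protocol 8.1. The general Normal/Low/High shift tables in SAP 9.5.2 cover selected parameters, but the text neither names ACR for them nor gives a 30 mg/g limit. The continuous summaries describe the group and do not count patients.

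**The case against.** The strongest reply is that this is a clear, reproducible choice. The 300 mg/g cut governs dose group and stratum and is also the macro-albuminuria boundary in Table 7, and no passage says Table 7 must govern shift tables. Figure 2 describes its albuminuria columns as persistent categories, whereas most of the shift tables rest on single worst values. All of that is fair. It shows that the rule is legitimate, not that it is the more informative of two scales the SAP already holds.

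The second reply is that albuminuria change is reported elsewhere. This stands in large part. SAP 9.5.1 gives geometric mean ratios with confidence intervals at each time point, SAP 9.5.1.1 adds ln(ACR)/eGFR, and off-treatment ACR is scheduled at Weeks 104 (B) and 108 (B). A reader might infer that the plan conceals a rise in albuminuria, or its reversal, below 300 mg/g. The documents do not support that: group-level movement is visible, and only the number of patients crossing 30 mg/g is missing.

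Third, a reader might take the albumin increase as an established effect in this population. Protocol 5.1.2.6 reports it in some patients with CKD and type 2 diabetes, not in ADPKD. The monitoring trigger in Protocol 9.1.6 is also far higher: more than a doubling that also exceeds 1000 mg/g.

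Fourth, a 30 mg/g cut brings noise. Four of the six tables use the worst on-treatment value, the maximum of up to 11 scheduled spot urines (Weeks 4, 8, 12, 24, 36, 48, 52, 64, 76, 88 and 100). Three of the six start from baseline, which SAP 6.4.5 defines as the last value before dosing. Some crossings will be chance. This stands as a small cost; it applies to both arms, and the placebo column puts it in context.

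**Conclusion.** The point holds as a limited reporting gap. Followed as written, the six ACR shift tables count no move between normo- and micro-albuminuria in either direction, and a patient starting below 30 mg/g appears only after more than a tenfold rise. The tables are descriptive, so no efficacy estimate, sample size, power or type I error rate changes.

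Two stronger statements should not be drawn. The fold changes in the examples are not ceilings: 10 to 300 mg/g is thirtyfold, and a lower start would give more. Nor can one say what share of patients sits in the ≤300 cell. The 20% rule in SAP Section 8 only decides whether a stratification factor enters the efficacy models; it gives no ACR distribution.

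The conclusion rests on the readable text. Most of the endpoint list and parts of SAP 8.6 are blacked out, so a three-level ACR analysis there cannot be excluded. The shift-table rule itself is fully legible.

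**What to change.** In SAP 9.5.2, change the ACR cross-reference from Section 6.5.5.1 to the Table 7 categories in Section 6.5.4.1 (<30, 30 to ≤300, >300 mg/g) for all six comparisons. Leave the two-level split in place for the baseline and stratum displays.

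The cost is one edited cross-reference and one more row and column per table, from data already collected. In the worst-value tables, add a footnote that some crossings of 30 mg/g are expected by chance in both arms and should be read against placebo.

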9.5.2.1. Transaminases

Evaluation of Drug-Induced Serious Hepatotoxicity (eDISH) plots are generated for ALT and AST versus TBL.

The number and percentage of patients meeting the following thresholds (Table 10) at any time during the study are summarized by the maximum dosage received. The pre-specified thresholds are consistent with FDA guidance.

Table 10: PRE-SPECIFIED THRESHOLD LEVELS FOR TRANSAMINASES

Lab Parameter	Threshold
ALT, AST	$\geq 3 \times$ upper limit of normal (ULN) and $<5 \times$ ULN

Lab Parameter	Threshold
	$\geq 5 \times \text{ULN}$ and $< 10 \times \text{ULN}$
	$\geq 10 \times \text{ULN}$ and $< 20 \times \text{ULN}$
	$\geq 20 \times \text{ULN}$
	$\geq 5 \times \text{ULN}$ for more than 2 weeks
TBL	$\geq \text{ULN}$ and $\leq 1.5 \times \text{ULN}$
	$> 1.5 \times \text{ULN}$ and $\leq 2 \times \text{ULN}$
	$> 2 \times \text{ULN}$
ALT, AST, TBL	ALT or AST $> 3 \times \text{ULN}$ and TBL $> 1.5 \times \text{ULN}$
	ALT or AST $> 3 \times \text{ULN}$ and TBL $> 2 \times \text{ULN}$
ALT, AST, TBL, International normalized ratio (INR)	$> 3 \times \text{ULN}$ and (TBL $> 2 \times \text{ULN}$ or INR > 1.5)
ALP	$> 1.5 \times \text{ULN}$

A listing of subjects with abnormal ALT, AST, or TBL will also be provided.

9.7. Vital Signs

Vital signs assessments include systolic blood pressure (SBP, mmHg) and diastolic blood pressure (DBP, mmHg), body temperature (°C), heart rate (HR, bpm), height (cm), weight (kg), and BMI (kg/m²). Vital signs are summarized at baseline and at each time point along with the change from baseline by treatment. Boxplots and line graphs of change from baseline over time for blood pressure are plotted.

In addition, a summary table is provided for the number and percentage of patients meeting a following pre-specified post baseline on-treatment blood pressure change categories:

- SBP (mm Hg):
 - Maximum increase from baseline: ≥ 20 ; ≥ 40 ; ≥ 60
 - Maximum decrease from baseline: ≥ 20 ; ≥ 40
- DBP (mm Hg):
 - Maximum increase from baseline: ≥ 20 ; ≥ 40
 - Maximum decrease from baseline: ≥ 20

9.8. 24-hr ABPM Sub-study

A subset of patients who consent to the 24-hour ambulatory blood pressure monitoring (ABPM) sub-study will have systolic blood pressure, diastolic blood pressure, pulse pressure and heart rate collected during 24-hour periods as specified in [Table 2](#). Observed values and change from baseline will be summarized at baseline and at analysis visits Week 12, Week 48 and Week 88 for each 24-hour ABPM assessment using the following 24-hour parameters: overall mean, daytime mean, and nighttime mean. Descriptive summaries will include confidence intervals.

The 24-hour ABPM parameters will be calculated as specified in [Table 11](#). For each 24-hour period, calculation of the average values is the sum of all valid ambulatory blood pressure measurements divided by the number of all valid blood pressure measurements, within the range of time specified for the parameter. Categorical summaries for systolic blood pressure and diastolic blood pressure described in [Section 9.7](#) will also be performed.

Table 11: 24-HOUR ABPM PARAMETERS

Parameter	Calculation
Overall (24-hour) SBP, DBP mean	average of all valid measurements taken from the patient’s ambulatory blood pressure monitoring device
Daytime SBP, DBP mean	average of all valid measurements taken from 6 am to 10 pm
Nighttime SBP, DBP mean	average of all valid measurements taken from 10 pm to 6 am next day

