#### **5.1.2.7. Impact on Adolescent Growth (Weight and Height)**

Impacts on weight and height gain were observed in bardoxolone methyl-treated adolescent patients (ages 12-17 years) with Alport syndrome (study 402-C-1603 CARDINAL) when compared to placebo-treated adolescent patients. In this study, a total of 23 adolescents were enrolled, where 11 and 12 were randomized to bardoxolone methyl and placebo, respectively.

In bardoxolone methyl treated adolescents, both weight and height at baseline were relatively higher than placebo treated adolescents. Bardoxolone methyl treated patients had a mean baseline weight of 65.50 kg (SD 10.193, median 63.90 kg, min/max 52.5/81.3 kg), while placebo

treated adolescents had a mean baseline weight of 57.79 kg (SD 16.020, median 59.80 kg, min/max 29.5/76.3 kg). A change from baseline using the last on treatment value available for weight showed a mean weight decrease of -1.41 kg (SD 5.260, median -2.30 kg, min/max -10.9 to 6.8 kg) for bardoxolone methyl treated adolescents and a mean weight increase of +2.26 kg (SD 4.153, median +2.25 kg, min/max -5.7 to +8.2 kg) for placebo treated adolescents.

Bardoxolone methyl treated adolescents at baseline had a mean height of 171.7 cm (SD 5.90, median 172.0 cm, min/max 165/183 cm), while placebo treated adolescents had a mean height of 166.3 cm (SD 14.94, median 169.5 cm, min/max 136/186 cm). A change from baseline using the last on treatment value available showed a mean height increase of +1.1 cm (SD 1.13, median +1.0 cm, min/max 0 to 3 cm) for bardoxolone methyl treated adolescents, compared with a mean height increase of +2.4cm (SD 3.65, median 0.6 cm, min/max -1 to +11cm) for placebo treated adolescents.

Bardoxolone methyl treated adolescents at baseline had a mean BMI of 22.1 kg/m^2 (SD 2.11, median 22.3 kg/m^2, min/max 19/25 kg/m^2), while placebo treated adolescents at baseline had a mean BMI of 20.5 kg/m^2 (SD 3.63, median 20.3 kg/m^2, min/max 16/26 kg/m^2). Overall, in bardoxolone methyl treated adolescents, BMI changes from baseline to last value on treatment showed a mean decrease of -0.5 kg/m^2 (SD 1.40, median -0.8 kg/m^2, min/max -3/+2 kg/m^2), compared with a mean BMI increase in placebo treated adolescents of 0.3 kg/m^2 (SD 1.15, median 0.3 kg/m^2, min/max -2/+2 kg/m^2).

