In Study 402-C-1603 phase 3, the number of adolescent subjects was relatively small; therefore, a firm conclusion cannot be derived. Overall, no other concerning differences in the safety profile were identified in patients 12 to < 18 years of age compared to adult patients randomized to receive bardoxolone methyl (total: n=77; adults: n=66) or to receive placebo (total: n=80; adults: 68).

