### 9.1.10 Monitoring Growth and Sexual Development in Adolescents

Growth and sexual development will be assessed through an evaluation of height, weight, and Tanner Staging. See the Study Reference Manual for details on the Tanner staging.

Body weight should be measured daily by patients/caregivers using a provided weighing scale. Weight and height will also be measured at all site visits, as outlined in Section 9.10.7. Patients should be instructed to inform the site if there is an observed weight loss of more than 3 pounds (1.4kg) in between clinic visits (Section 9.1.1).

The Medical Monitor will routinely evaluate both weight and height entered into the clinical database of adolescents and will inform the investigator to initiate further evaluation if there is a weight loss of  $\geq 5\%$  or lack of expected growth per growth charts.

Sexual maturity will be assessed by the investigator using Tanner Staging. If any abnormal patterns of sexual maturity are identified on evaluation of Tanner Staging, the Medical Monitor should be notified for additional discussion.

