3.2.4. Safety Endpoints

- Frequency, intensity, and relationship to study drug of adverse events (AEs) and serious adverse events (SAEs) and change from baseline in the following assessments: vital sign measurements, 12-lead electrocardiograms (ECGs), clinical laboratory measurements, pediatric growth (height and weight), and sexual maturity using Tanner staging.

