9. SAFETY AND TOLERABILITY

Safety and tolerability are evaluated by AEs, SAEs, clinical laboratory test results, body weight, vital signs, 12-lead ECG findings. All analyses of the safety data are performed using the safety analysis set. Descriptive statistics are presented by treatment group assignment in the safety analysis set. Statistical testing is not performed for safety analyses unless otherwise specified. On-treatment values are summarized according to the analysis study windows in Section 6.5.2; Off-treatment values are summarized according to the analysis study windows in Section 6.5.2.1. Safety data summaries are grouped by treatment.

Continuous safety parameters (including selected clinical chemistries and vital signs) may be summarized using the methodology described in Section 8.4.1, and Section 8.5.1. Only the visit windows outlined in Table 4 and Table 5 are included in these analyses.

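### In the visible SAP, adolescent growth has no adolescent-only analysis: weight and BMI are pooled with adults, and height change stays on a raw scale

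*SAP*

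**What the plan says.** Protocol 6.2.4 and SAP 3.2.4 list among the safety endpoints change from baseline in "pediatric growth (height and weight), and sexual maturity using Tanner staging". The Version 7 summary of changes says this was added after health authority feedback about monitoring adolescents.

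SAP 9.7 counts height (cm), weight (kg) and BMI as vital signs and states that "Vital signs are summarized at baseline and at each time point along with the change from baseline by treatment". The population is set in SAP Section 9: "All analyses of the safety data are performed using the safety analysis set". The same section adds that "Statistical testing is not performed for safety analyses unless otherwise specified". The visible text gives no table restricted to patients under 18, no standardised score and no Tanner summary. The split at age 18 is named only as a baseline characteristic (SAP 7.3).

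The schedules of assessments in both documents measure adult height at Screen A only and adolescent height at every listed visit. Weight is taken at clinic visits in all patients, and BMI is calculated each time weight is recorded (Protocol 9.10.7). For monitoring, Protocol 9.1.10 has the Medical Monitor look for "lack of expected growth per growth charts" in individual adolescents. The SAP has no counterpart to that reference.

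**The concern.** An endpoint about growth in minors needs an analysis in which minors can be seen. The stated method falls short in two ways.

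First, weight and BMI change are averaged over everyone aged 12 to 70. The adult result then dominates, and a different result in adolescents cannot be read from the table.

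Second, raw height change mixes patients at very different points of growth. Protocol 5.1.2.7 shows this in adolescents with Alport syndrome: height change on placebo ran from -1 to +11 cm. In the drug arm "both weight and height at baseline were relatively higher than placebo treated adolescents". Randomisation is stratified by eGFR, tolvaptan use and ACR (SAP 4.4), not by age, so in a small group a chance imbalance in age or pubertal stage could create or hide a difference.

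At stake is whether the trial adds anything readable to the earlier data, from which, the protocol says, "a firm conclusion cannot be derived".

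**Working it through.** The documents give no sample size, power or precision for growth, so there is no growth figure to reproduce. The only power statement concerns eGFR: 425 per arm, difference 2.3, SD 12 and two-sided 0.05 give 79.8%, in line with the stated 80%. It has no bearing on this point.

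**Inputs** (Protocol 5.1.2.7, adolescents, 11 on drug and 12 on placebo, change to last on-treatment value):
- Weight: -1.41 kg (SD 5.260) against +2.26 kg (SD 4.153).
- BMI: -0.5 against +0.3 kg/m².
- Height: +1.1 cm (SD 1.13, median +1.0) against +2.4 cm (SD 3.65, median +0.6).
- Baseline height: 171.7 against 166.3 cm. Baseline weight: 65.50 against 57.79 kg.

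**1. Weight and BMI in the pooled table.** The adolescent differences are -1.41 - 2.26 = -3.67 kg and -0.5 - 0.3 = -0.8 kg/m². With adolescent share f, equal in both arms:

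all-patient difference = f × (adolescent difference) + (1 - f) × (adult difference).

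The adolescent contribution to weight is f × 3.67 kg in size:
- f = 1%: 0.04 kg
- f = 2%: 0.07 kg
- f = 5%: 0.18 kg
- f = 10%: 0.37 kg

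For BMI it is 0.01 × 0.8 = 0.008 to 0.10 × 0.8 = 0.08 kg/m².

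As an illustration, take an adult difference of -3 kg, borrowed from the pulmonary hypertension figure in Protocol 5.1.2.4, and f = 5%. With the adolescent effect, 0.05 × (-3.67) + 0.95 × (-3) = -3.03 kg. With no adolescent effect, 0.95 × (-3) = -2.85 kg. A reader could not tell these apart.

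**2. Height rows.** Adults have no post-baseline height, so the change rows hold adolescents only and are not diluted. The baseline row includes adult heights and is therefore not comparable with the rows below it.

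**3. Noise on the raw height scale.** The difference is 1.1 - 2.4 = -1.3 cm. SE = √(1.13²/11 + 3.65²/12) = √(0.116 + 1.110) = 1.11 cm, and 1.3/1.11 = 1.17. The Welch 95% interval is -3.7 to 1.1 cm. The medians differ in the opposite direction (+1.0 against +0.6), so a few fast growers on placebo set the mean. The arms also began 171.7 - 166.3 = 5.4 cm and 65.50 - 57.79 = 7.7 kg apart.

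**4. The same scale in this trial.** The pooled SD is √[(10 × 1.13² + 11 × 3.65²)/21] = 2.75 cm. The 95% half-width for n adolescents in total is 1.96 × 2.75 × √(4/n): 2.4 cm for n = 20 and 1.7 cm for n = 40 (both n assumed). Each exceeds the 1.3 cm difference seen before.

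**The case against.** The strongest reply has five parts.

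- **Height is not diluted.** A reader might infer from the whole-safety-set wording that adults swamp height change. The measurement schedule rules that out. This stands; dilution applies to weight and BMI only.
- **Allocation is randomised.** A reader might infer that age mix biases the comparison. It adds noise and possible chance imbalance, not systematic bias. This stands.
- **Follow-up is short and development has ended.** Patients aged 12 to 17 became eligible with protocol Version 6, dated 04 February 2022. SAP Section 2 puts the study drug termination date at 10 May 2023, 460 days or about 66 weeks later. No adolescent could have reached Week 100 on drug. This stands and lowers the severity.
- **Standardising does not cure small numbers.** Protocol 5.1.2.7 attributes its inconclusive result to the small group, not to raw units, and gives no ages by arm. That the taller arm had less growth left is an inference. This stands too.
- **Safeguards exist.** SAP 6.2 reports medians, quartiles and ranges, by-patient listings are planned, growth is monitored individually, and the data monitoring committee sees unblinded safety data. These help, particularly for skewed height change, but none separates adolescent from adult weight and BMI in a summary by arm.

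The visible numbering passes from 9.5.2.1 to 9.7, so the content of a Section 9.6 is unknown. That calls for caution. However, height, weight and BMI are openly assigned to 9.7, and the list of tables shows no numbered table for growth.

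**Conclusion.** The point holds for the visible plan. For weight and BMI, the stated summary cannot show an adolescent effect: a 3.67 kg difference would move the pooled figure by 0.04 to 0.37 kg. For height, the change rows contain the right patients, but the scale is noisy across ages and the baseline row mixes in adults.

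This rests on assumed adolescent shares of 1% to 10%, balanced across arms, and on an adolescent effect as large as in the Alport data, where the weight difference itself was uncertain (95% interval -7.8 to 0.5 kg). The number of adolescents is not stated.

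A reader might go further and conclude that normal growth will determine the result whatever the drug does, or that a better analysis would settle whether the drug slows growth. The documents support neither: assignment is random, and the group is likely to be small with shortened follow-up. This is a minor point with a cheap improvement.

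**What to change.** In SAP 9.7, add a separate table by arm for patients under 18 at consent, giving height, weight and BMI as age- and sex-specific z-scores with change from baseline. Name the growth reference and state what is done once a patient passes its upper age. Add by-patient plots over time marked by baseline Tanner stage, and keep raw values in listings. Restrict the baseline height row that accompanies height change to the same patients.

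The cost is SAP wording, one derivation and a small descriptive table. Sex, height, weight and Day 1 Tanner stage are already collected, and SAP 6.5.4 already uses age and height at the time of each creatinine sample. Safety output is descriptive, so no error rate is affected. The SAP says it will be finalised before database lock, so the change can still be prespecified. The downside is limited yield: with few adolescents and short follow-up, the table will describe growth by arm and will not by itself answer whether the drug slows it.
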